4.2 TARGET LESIONS (TL)

4.2.1 Documentation of target lesions

A maximum of 5 measurable lesions, with a maximum of 2 lesions per organ (including lymph nodes), representative of all lesions involved should be identified as TL at baseline. Target lesions should be selected on the basis of their size (longest diameter for non nodal lesions or short axis for nodal lesions), but in addition should be those that lend themselves to reproducible repeated measurements. It may be the case that, on occasion, the largest lesion does not lend itself to reproducible measurement in which circumstance the next largest lesion, which can be measured reproducibly, should be selected.

The site and location of each TL should be documented as well as the longest diameter for non nodal lesions (or short axis for lymph nodes). All measurements should be recorded in

millimeters. At baseline the sum of the diameters for all TL will be calculated and reported as the baseline sum of diameters. At follow-up visits the sum of diameters for all TL will be calculated and reported as the follow-up sum of diameters.

Special cases:

- For TL measurable in 2 or 3 dimensions, always report the longest diameter. For pathological lymph nodes measurable in 2 or 3 dimensions, always report the short axis.
- If the CT/MRI slice thickness used is > 5mm, the minimum size of measurable disease at baseline should be twice the slice thickness of the baseline scan.
- If a lesion has completely disappeared, the longest diameter should be recorded as 0 mm.
- If a TL splits into two or more parts, then record the sum of the diameters of those parts.
- If two or more TL merge then the sum of the diameters of the combined lesion should be recorded for one of the lesions and 0 mm recorded for the other lesion(s).
- If a TL is believed to be present and is faintly seen but too small to measure, a default value of 5 mm should be assigned. If an accurate measure can be given, this should be recorded, even if it is below 5 mm.
- If a TL cannot be measured accurately due to it being too large, provide an estimate of the size of the lesion.
- When a TL has had any intervention eg, radiotherapy, embolisation, surgery etc., during the study, the size of the TL should still be provided where possible.

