4.2.2 Evaluation of target lesions

This section provides the definitions of the criteria used to determine objective tumour visit response for TL.

App. Table 2 Evaluation of target lesions

Complete Response (CR)	Disappearance of all target lesions since baseline. Any pathological lymph nodes selected as target lesions must have a reduction in short axis to < 10 mm.
Partial Response (PR)	At least a 30% decrease in the sum of the diameters of TL, taking as reference the baseline sum of diameters
Stable Disease (SD)	Neither sufficient shrinkage to qualify for PR nor sufficient increase to qualify for PD
Progressive Disease (PD)	At least a 20% increase in the sum of diameters of target lesions, taking as reference the smallest sum on study (this includes the baseline sum if that is the smallest on study). In addition to the relative increase of 20%, the sum must also demonstrate an absolute increase of at least 5mm.
Not Evaluable (NE)	Only relevant if any of the target lesions were not assessed or not evaluable or had a lesion intervention at this visit. Note: If the sum of diameters meets the progressive disease criteria, progressive disease overrides not evaluable as a target lesion response

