4.4 NEW LESIONS

Details of any new lesions will also be recorded with the date of assessment. The presence of one or more new lesions is assessed as progression.

A lesion identified at a follow up assessment in an anatomical location that was not scanned at baseline is considered a new lesion and will indicate disease progression.

The finding of a new lesion should be unequivocal: ie, not attributable to differences in scanning technique, change in imaging modality or findings thought to represent something other than tumour.

If a new lesion is equivocal, for example because of its small size, the treatment and tumour assessments should be continued until the new lesion has been confirmed. If repeat scans confirm there is a new lesion, then the progression date should be declared using the date of the initial scan.

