3.2.2.1 Target lesions – site investigator data

For each patient, the site investigator will identify measurable tumour lesions at baseline (representative of all lesions involved and suitable for accurate repeated measurement) and these are referred to as TLs. If more than one baseline scan is recorded then measurements from the one that is closest and prior to randomisation will be used to define the baseline sum of diameters of TLs.

All other lesions (or sites of disease) not recorded as TL will be identified as NTLs at baseline. Measurements are not required for these lesions, but their status will be followed at subsequent visits.

Table 1 TL Visit Responses (RECIST 1.1)

Visit Responses	Description
Complete response (CR)	Disappearance of all TLs. Any pathological lymph nodes selected as TLs must have a reduction in short axis to <10mm.
Partial response (PR)	At least a 30% decrease in the sum of diameters of TLs, taking as reference the baseline sum of diameters as long as criteria for PD are not met.
Progressive disease (PD)	A $\geq 20\%$ increase in the sum of diameters of TLs and an absolute increase of $\geq 5\text{mm}$, taking as reference the smallest sum of diameters since treatment started including the baseline sum of diameters.
Stable disease (SD)	Neither sufficient shrinkage to qualify for PR nor sufficient increase to qualify for PD.
Not evaluable (NE)	Only relevant in certain situations (i.e. if any of the TLs were not assessed or not evaluable or had a lesion intervention at this visit; and scaling up could not be performed for lesions with interventions). Note: If the sum of diameters meets the progressive disease criteria, progressive disease overrides not evaluable as a TL response.
Not applicable (NA)	No TLs are recorded at baseline.

Rounding of TL data

For calculation of PD and PR for TLs percentage changes from baseline and previous minimum should be rounded to one decimal point before assigning a TL response. For example 19.95% should be rounded to 20.0% but 19.94% should be rounded to 19.9%.

Missing TL data

For a visit to be evaluable all TL measurements should be recorded. However, a visit response of PD should still be assigned if any of the following occurred:

- A new lesion is recorded
- A non-target lesion (NTL) visit response of PD is recorded

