Scaling (applicable only for irradiated lesions/lesion intervention)

If $> 1/3$ of TL measurements are missing because of intervention then the TL response will be NE, unless the sum of diameters of non-missing TL would result in PD (i.e. if using a value of 0 for missing lesions, the sum of diameters has still increased by 20% or more compared to nadir and the sum of TLs has increased by $\geq 5\text{mm}$ from nadir).

If $\leq 1/3$ of the TL measurements are missing because of intervention then the results will be scaled up (based on the sizes at the nadir visit to give an estimated sum of diameters and this will be used in calculations; this is equivalent to comparing the visit sum of diameters of the non-missing lesions to the nadir sum of diameters excluding the lesions with missing measurements).

Lesions that split in two

If a TL splits in two, then the LDs of the split lesions should be summed and reported as the LD for the lesion that split.

Lesions that merge

If two TLs merge, then the LD of the merged lesion should be recorded for one of the TL sizes and the other TL size should be recorded as 0cm.

Change in method of assessment of TLs

Computed tomography (CT), magnetic resonance imaging (MRI) and clinical examination are the only methods of assessment that can be used within a trial, with CT and MRI being the preferred methods and clinical examination only used in special cases. If a change in method

of assessment occurs, between CT and MRI this will be considered acceptable and no adjustment within the programming is needed.

If a change in method involves clinical examination (e.g. CT changes to clinical examination or vice versa), any affected lesions should be treated as missing.

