New lesions will be identified via a Yes/No tick box. The absence and presence of new lesions at each visit should be listed alongside the TL and NTL visit responses.

A new lesion indicates progression so the overall visit response will be PD irrespective of the TL and NTL response.

If the question ‘Any new lesions since baseline’ has not been answered with Yes or No and the new lesion details are blank this is not evidence that no new lesions are present, but should not overtly affect the derivation. Note: This scenario (i.e. whereby new lesion response is NE), should only occur in exceptional cases, as missing data for the new lesion field should always be queried.

Symptomatic progression is not a descriptor for progression of NTLs: it is a reason for stopping study therapy and will not be included in any assessment of NTLs.

Patients with ‘symptomatic progression’ requiring discontinuation of treatment without objective evidence of disease progression at that time should continue to undergo tumour assessments where possible until objective disease progression is observed.

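### Appendix F's recording rule for merged target lesions conflicts with its own longest-diameter rule and with the SAP, and taken literally can turn stable disease into site-assessed progression

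*Protocol*

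**What the plan says.** The special cases in Protocol Appendix F 4.2.1 contain two instructions that do not fit together.

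- The first bullet is general: "For TL measurable in 2 or 3 dimensions, always report the longest diameter". It continues with the short axis for pathological lymph nodes.
- The merge bullet reads: "If two or more TL merge then the sum of the diameters of the combined lesion should be recorded for one of the lesions", with 0 mm for the other lesion or lesions.

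SAP 3.2.2.1, under site investigator data, states: "If two TLs merge, then the LD of the merged lesion should be recorded for one of the TL sizes". The other size is entered as zero. The SAP sentence covers two lesions only, gives no exception for nodes and writes the zero in centimetres.

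The progression thresholds are the same in both documents. Appendix F 4.2.2 requires "At least a 20% increase in the sum of diameters of target lesions, taking as reference the smallest sum on study", and adds that "the sum must also demonstrate an absolute increase of at least 5mm". SAP Table 1 uses the same 20% and 5 mm, "taking as reference the smallest sum of diameters since treatment started including the baseline sum of diameters".

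SAP 3.2.2 bases investigator endpoints on the tumour measurements supplied by the site, not on the investigator's own response tick box. SAP Section 6 declares no change from the protocol.

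**The concern.** A merged lesion is a single lesion, so a sum of its diameters has no defined meaning. The phrase suits the split-lesion bullet just above it, where the parts are added, and may have been carried over from there. Nothing else in either document explains how to sum the diameters of one combined mass. A site can take it literally in two ways: add the diameters of the component lesions, or add two diameters of the merged mass.

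Protocol Section 5 tells sites to complete the eCRF as the protocol specifies. The SAP's merge sentence therefore does not reach the person entering the number. Once a summed value is in the database, no SAP step can recover the longest diameter. What is at stake is a site-assessed progression, with its date, that arises from the recording rule and not from tumour growth.

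**Working it through.** The plan gives no figure on this point to reproduce. The check applies the shared progression rule to one hypothetical scan under each reading. All lesion sizes are assumptions, because the documents give none. Non-target disease is taken as not progressing, with no new lesions, so the target-lesion response is the visit response.

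**Rule.** Percentage change = 100 x (sum at visit - nadir sum) / nadir sum, rounded to one decimal as in SAP 3.2.2.1. Progression needs at least +20% and at least +5 mm. Partial response needs at least -30% from baseline.

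**Example 1.** Target lesions of 20, 20 and 15 mm; baseline = nadir = 55 mm. The first two grow to 26 mm each and merge into a mass with longest diameter 34 mm and second diameter 22 mm.

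**Example 2.** Two target lesions of 20 mm; baseline = nadir = 40 mm. Both grow to 25 mm and merge with longest diameter 40 mm; the second diameter is taken as 25 mm.

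| Reading | Example 1 | Example 2 |
|---|---|---|
| Longest diameter (SAP; Appendix F first bullet) | 34+0+15 = 49 mm; -6/55 = -10.9%; stable | 40+0 = 40 mm; 0.0%; stable |
| Component diameters added | 26+26+15 = 67 mm; +12/55 = +21.8%; progression | 25+25 = 50 mm; +10/40 = +25.0%; progression |
| Longest plus second diameter | 34+22+15 = 71 mm; +16/55 = +29.1%; progression | 40+25 = 65 mm; +25/40 = +62.5%; progression |

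**How far this generalises.** Take two 20 mm lesions (nadir 40 mm) growing by a factor g and overlapping by a fraction f of one diameter. Each component is 20g, so the component sum is 40g and the longest diameter is (2 - f) x 20g.

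- The component sum gives progression when 40g >= 48, that is g >= 1.2.
- The longest diameter gives progression when (2 - f) x 20g >= 48, that is g >= 2.4/(2 - f).
- The two disagree only for 1.2 <= g < 2.4/(2 - f). The upper limit is 1.20 at f = 0 (no disagreement), 1.26 at f = 0.1, 1.33 at f = 0.2, 1.41 at f = 0.3 and 1.50 at f = 0.4.

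Under the component reading the rules therefore agree when growth is below 20%, or when overlap is slight for the growth seen. If instead the longest diameter is added to a second diameter equal to one component, Appendix F gives progression over the whole range examined (growth 0 to 40%, overlap 0 to 40%). That includes no growth at all: at f = 0.4 and g = 1, 32 + 20 = 52 mm, or +30%.

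Example 1 implies an overlap of 2 x 26 - 34 = 18 mm if the lesions lie in line, which is more than the range covers. Example 2 implies 10 mm, or 40% of one diameter, which is its upper edge.

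**The case against.** The strongest reply is that the phrase is a drafting slip. Elsewhere in Appendix F 4.2.1 a sum of diameters is taken across lesions or across split parts, and a site reading the merge bullet with the first bullet could well enter the longest diameter. The conflict would then vanish in practice. That is possible, but the text does not say so and no other passage settles it. The reply does weaken the longest-plus-second-diameter reading, which is the most extreme; the point does not rest on it.

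Several stronger inferences are tempting and are not supported:

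- **That the same data would yield two verdicts.** They would not. The site enters one value and the SAP derives one response from it. The fault is a contradictory recording instruction.
- **That primary PFS is compromised.** SAP 3.2.1 takes visit responses from the central reviewers without programmatic derivation, and Appendix F Section 1 limits itself to investigator assessment. A site progression not shared centrally might lead to censoring, but this is not certain. Protocol 5.1.1 allows a further assessment to be requested, SAP 3.3.1 still counts a death within the allowed gap, and SAP 4.2.5 tabulates disagreements and allows an imputed event if they are important.
- **That a false progression automatically ends treatment.** Protocol 3.8 says patients may be discontinued and makes an exception where the investigator judges that the patient is benefiting.
- **That the futility decision is at risk.** SAP 5.2 records an April 2019 committee decision after the planned look in the non-HRRm population, so that look appears to be past. The look in the non-BRCAm HRRm population is optional.
- **That the dating of new lesions also conflicts.** Appendix F 4.4 sets the date of a confirmed equivocal lesion at the initial scan, SAP 3.2 refers to Appendix F for response definitions, and SAP 3.2.2 uses the earliest scan date of the triggering component. At most a programming detail is missing.

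**Conclusion.** The contradiction stands in the current text and is undeclared. A site that follows the merge bullet literally can generate progression where the longest-diameter rule gives stable disease, and this is shown under both literal readings. Under the milder, component-diameter reading it needs growth of at least 20% together with enough overlap.

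The size is small. It concerns only patients whose target lesions merge, probably few, although the documents give no frequency. Direct reach is site-assessed progression, the investigator-based sensitivity analyses of PFS, response rate, duration of response and tumour size, and any remaining Week 8 non-progression look. In such a look, with about 25 patients per arm, one misclassified patient moves the proportion by 1/25 = 4 percentage points. The conclusion assumes that some sites would take the wording literally, and the numerical examples assume the lesion sizes shown. This is a minor point, worth correcting because the correction is cheap and a wrong entry cannot be repaired in the analysis.

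**What to change.** Replace the merge bullet in Appendix F 4.2.1 with: if two or more target lesions merge, record the longest diameter of the merged lesion (short axis if nodal) for one of them and 0 mm for the other or others.

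Put the same sentence in SAP 3.2.2.1. The present SAP wording cannot simply be copied into the protocol, because it covers only two lesions, says nothing about nodes and uses centimetres. Correcting Appendix F alone would leave a difference for merged nodes.

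Send sites a short note, and ask them to check any merged lesion already entered. The cost is one sentence in each document and the note. Sample size, analysis methods and the central review are unchanged.

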4.2.2 Evaluation of target lesions

This section provides the definitions of the criteria used to determine objective tumour visit response for TL.

App. Table 2 Evaluation of target lesions

Complete Response (CR)	Disappearance of all target lesions since baseline. Any pathological lymph nodes selected as target lesions must have a reduction in short axis to < 10 mm.
Partial Response (PR)	At least a 30% decrease in the sum of the diameters of TL, taking as reference the baseline sum of diameters
Stable Disease (SD)	Neither sufficient shrinkage to qualify for PR nor sufficient increase to qualify for PD
Progressive Disease (PD)	At least a 20% increase in the sum of diameters of target lesions, taking as reference the smallest sum on study (this includes the baseline sum if that is the smallest on study). In addition to the relative increase of 20%, the sum must also demonstrate an absolute increase of at least 5mm.
Not Evaluable (NE)	Only relevant if any of the target lesions were not assessed or not evaluable or had a lesion intervention at this visit. Note: If the sum of diameters meets the progressive disease criteria, progressive disease overrides not evaluable as a target lesion response

4.3 NON TARGET LESIONS (NTL)

4.3.1 Evaluation of non target lesions

All other lesions (or sites of disease) not recorded as TL should be identified as NTL at baseline. Measurements are not required for these lesions, but their status should be followed at subsequent visits. At each visit an overall assessment of the NTL response should be recorded by the Investigator. This section provides the definitions of the criteria used to determine and record overall response for NTL at the investigational site at each visit.

App. Table 3 Evaluation of Non Target Lesions

Complete Response (CR)	Disappearance of all non target lesions since baseline. All lymph nodes must be non pathological in size (< 10 mm short axis).
Non CR/Non PD	Persistence of one or more NTL
Progression (PD)	Unequivocal progression of existing non target lesions. Unequivocal progression may be due to an important progression in one lesion only or in several lesions. In all cases the progression MUST be clinically significant for the physician to consider changing (or stopping) therapy.
Not Evaluable (NE)	Only relevant when one or some of the non target lesions were not assessed and, in the Investigator's opinion, they are not able to provide an evaluable overall non target lesion assessment at this visit.

Note: For patients without target lesions at baseline, this is relevant if any of the non target lesions were not assessed at this visit and the progression criteria have not been met.

To achieve 'unequivocal progression' on the basis of non target lesions, there must be an overall level of substantial worsening in non target disease such that, even in presence of SD or PR in target lesions, the overall tumour burden has increased sufficiently to merit discontinuation of therapy. A modest 'increase' in the size of one or more non target lesions is usually not sufficient to qualify for unequivocal progression status.

4.4 NEW LESIONS

Details of any new lesions will also be recorded with the date of assessment. The presence of one or more new lesions is assessed as progression.

A lesion identified at a follow up assessment in an anatomical location that was not scanned at baseline is considered a new lesion and will indicate disease progression.

The finding of a new lesion should be unequivocal: ie, not attributable to differences in scanning technique, change in imaging modality or findings thought to represent something other than tumour.

If a new lesion is equivocal, for example because of its small size, the treatment and tumour assessments should be continued until the new lesion has been confirmed. If repeat scans confirm there is a new lesion, then the progression date should be declared using the date of the initial scan.

4.5 SYMPTOMATIC DETERIORATION

Symptomatic deterioration is not a descriptor of an objective response: it is a reason for stopping study therapy.

Patients with ‘symptomatic deterioration’ requiring discontinuation of treatment without objective evidence of disease progression at that time should continue to undergo tumour assessments where possible until objective disease progression is observed.

4.6 EVALUATION OF OVERALL VISIT RESPONSE

The overall visit response will be derived using the algorithm shown in Table 4.

App. Table 4 Overall Visit Response

Target lesions	Non Target lesions	New Lesions	Overall response
CR	CR	No	CR
CR	NA	No	CR
CR	Non CR/Non PD	No	PR
CR	NE	No	PR
PR	Non PD or NE	No	PR
SD	Non PD or NE	No	SD
NE	Non PD or NE	No	NE
PD	Any	Yes or No	PD
Any	PD	Yes or No	PD
Any	Any	Yes	PD

CR = complete response, PR = partial response, SD = stable disease, PD = progressive disease, NE = not evaluable, NA = not applicable (only relevant if there were no NTLs at baseline).

5. CENTRAL REVIEW

The Contract Research Organisation (CRO) appointed by AstraZeneca to perform the independent central review for this study will provide specification for radiological imaging protocols in standard acquisition guidelines documentation.

Appendix G ECOG Performance Status

These scales and criteria are used by doctors and researchers to assess how a patient's disease is progressing, assess how the disease affects the daily living abilities of the patient, and determine appropriate treatment and prognosis. They are included here for health care professionals to access.

ECOG PERFORMANCE STATUS*

Grade	ECOG
0	Fully active, able to carry on all pre-disease performance without restriction
1	Restricted in physically strenuous activity but ambulatory and able to carry out work of a light or sedentary nature, eg, light house work, office work
2	Ambulatory and capable of all selfcare but unable to carry out any work activities. Up and about more than 50% of waking hours
3	Capable of only limited selfcare, confined to bed or chair more than 50% of waking hours
4	Completely disabled. Cannot carry on any selfcare. Totally confined to bed or chair
5	Dead

* As published in Am. J. Clin. Oncol.:

Appendix H Not applicable following CSPv6.0 provided there has been a minimum washout period of 10 days since the final dose of AZD1775: Disallowed Medications and Medications to be Administered with Caution

DISALLOWED MEDICATIONS AND MEDICATIONS TO BE ADMINISTERED WITH CAUTION

Formal drug-drug interaction studies have not yet been performed with AZD1775, therefore, the potential for drug-drug interaction described in this protocol are based on findings from *in vitro* studies and clinical experience.

In vitro data has shown that AZD1775 is metabolised predominantly by CYP3A4, with an FMO3 and/or FMO5 component. As a result, there is potential for the exposure of AZD1775 to be affected by drugs which inhibit or induce the metabolism of CYP3A4. In the clinic, co-administration of AZD1775 with the moderate CYP3A4 inhibitor, aprepitant, resulted in a 40% increase in the plasma levels of AZD1775. Drugs known to be moderate to strong inhibitors/inducers of CYP3A4 are therefore prohibited for use in the current study, including aprepitant.

In vitro data suggests that AZD1775 may be a weak reversible inhibitor of CYP2C19 (IC₅₀ 12µM). Caution should therefore be exercised when AZD1775 is co-administered with agents that are sensitive substrates of CYP2C19, or substrates of this enzyme with a narrow therapeutic range.

Based on *in vitro* studies, AZD1775 has been shown to be a weak reversible inhibitor (IC₅₀ 14µM) and a time-dependent inhibitor of CYP3A4 (Kinact 0.061/min, Ki 6.04 µM). The full impact of the time dependent inhibition is currently unknown, however, modelling data has predicted an 8-10 fold increase in the exposure of sensitive CYP3A4 substrates when administered with AZD1775 (250 mg BID for 5 doses). To date, no significant DDI effects have been reported in the clinic that may be related to the TDI finding. However, sensitive CYP3A4 substrates or substrates of CYP3A4 with a narrow therapeutic window are prohibited.

AZD1775 has been shown to be a weak inducer of CYP1A2 *in vitro* (39% increase in activity of positive control). Given the nature of the AZD1775 dosing schedule, however, the risk of induction in the clinic is considered low. No specific precautions are recommended at this time, except to be initially vigilant when using substrates of CYP1A2 with a narrow therapeutic range.

Transporter studies (*in vitro*) have shown that AZD1775 is both a substrate and inhibitor (IC₅₀ 20 µM) of P-gp. Maximum impact of these finding is likely to occur for drugs administered orally at the same time as AZD1775. Caution should therefore be exercised when agents that are inhibitors or substrates of P-gp are administered concomitantly with AZD1775.

Recent *in vitro* transporter studies have shown AZD1775 to be an inhibitor of BCRP (IC₅₀ 5.1 µM). This finding is particularly relevant for drugs administered orally where exposure is normally limited by BCRP-mediated efflux, in particular some statins such as rosuvastatin. Other drugs where the disposition is mediated via BCRP should be administered with caution, dose modification considered or substituted by an alternative drug.

Use of metformin should be used with caution in this study as recent *in vitro* transporter data have shown AZD1775 is an inhibitor of Multidrug and Toxin Extruder 1 (MATE1) and MATE2K.

Caution should be used when administering drugs that are substrates of these transporters (eg, cimetidine, acyclovir, fexofenadine) as the clinical relevance of AZD1775 inhibition of the MATE pathway is not known in these compounds.

Herbal preparations/medications can be substrates, inhibitors and inducers, similar to any registered medication. Herbal preparations are therefore not allowed throughout the study. These herbal medications include, but are not limited to: St. John's wort, kava, ephedra (ma huang), ginkgo biloba, dehydroepiandrosterone (DHEA), yohimbe, saw palmetto, and ginseng.

In addition, any other drugs should be avoided at the Investigator's discretion if, in their opinion, the co-administration with AZD1775 may increase the risk of a clinically significant drug interaction.

A list of the main CYP3A4 substrates, inhibitors (strong and moderate) and inducers, CYP2C19 substrates, P-gp substrates, and inhibitors and BCRP substrates is shown below. This is not an exhaustive list and further details can be found at Expert Opin Drug Metab Toxicol (2013) 9(6):737-751.

CYP3A4 Inhibitors

Strong

Boceprevir	Ketoconazole
Clarithromycin	LCL161
Cobicistat (GS-9350)	Lopinavir
Conivaptan	Mibefradil
Danoprevir	Nefazodone
Elvitegravir	Nelfinavir
Fosamprenavir	Posaconazole
Grapefruit juice	Ritonavir
Idelalisib	Saquinavir
Indinavir	Telaprevir
Itraconazole	Telithromycin
	Tipranavir
	Troleandomycin
	Voriconazole

Moderate

ACT-178882	Imatinib
Amprenavir	Ledipasvir
Aprepitant	Lomitapide
Atazanavir	Netupitant
Casopitant	Schisandra sphenanthera
Ciprofloxacin	Tofisopam
Crizotinib	Verapamil
Darunavir	
Dronedarone	
Diltiazem	
Erythromycin	
FK1706	
Fluconazole	
Fosamprenavir	

Weak

Almorexant	I Linagliptin
Alprazolam	Lomitapide
AMD070	M100240
Amiodarone	Nilotinib
Amlodipine	Oral contraceptives
Atorvastatin	Pazopanib
Azithromycin	Peppermint oil
Berberine	Propiverine
Bicalutamide	Ranitidine
Blueberry juice	Ranolazine
Chlorzoxazone	Resveratrol
Cilostazol	Roxithromycin
Cimetidine	Seville orange juice
Clotrimazole	Simeprevir
Cranberry juice	Sitaxentan
Cyclosporine	Suvorexant
Daclatasvir	Tabimorelin
Delavirdine	Tacrolimus
Everolimus	Teriflunomide
Faldaprevir	Ticagrelor
Fluvoxamine	Tipranavir/ritonavir
Fosaprepitant (IV)	Tolvaptan
Ginkgo	Zileuton
Goldenseal	
GSK1292263	
GSK2248761	
Isoniazid	
Ivacaftor	
Lacidipine	

CYP3A4 Inducers (Strong and Moderate)

Avasimibe	Nafcillin
Bosentan	Phenobarbital
Carbamazepine	Phenytoin
Efavirenz	Rifabutin
Enzalutamide	Rifampin
Etravirine	Ritonavir
Genistein	Semagacestat
Lersivirine	St John's Wort
Lopinavir	Thioridazine
Mitotane	Tipranavir
Modafinil	

CYP3A4 Inducers (Weak)

Amprenavir	PA-824
Aprepitant	Pleconaril
Armodafinil	Prednisone
AZD 7325	Quercetin
Bexarotene	Raltegravir
Boceprevir	Ritonavir
Brivaracetam	Rufinamide
Clobazam	Sorafenib
Danshen	Stribild
Dexamethasone	Telaprevir
Echinacea	Terbinafine
Eslicarbazepine	Ticagrelor
Garlic	Ticlopidine
Gingko	Topiramate
Ginseng	Troglitazone
Glycyrrhizin	Vemurafenib
LCL161	Vicriviroc and ritonavir
Methylprednisolone	Vinblastine
Nevirapine	
Oritavancin	
Oxcarbazepine	

CYP3A and CYP3A4 Sensitive Substrates or Substrates with a Narrow Therapeutic Range

ABT-384	Dofetilide	Nisoldipine
Alfentanil		Paclitaxel
Aprepitant	Doxorubicin	Pazopanib
Alfuzosin	Ebastine	Perospirone
Almorexant	Eletriptan	Pimozide
Alpha-Dihydroergocryptine	Elvitegravir	Propafenone
Amiodarone	Eplerenone	Propofol
Aplaviroc	Ergotamine	Quetiapine
Aprepitant	Erlotinib	Quinidine
Astemizole	Etoposide	Ranolazine
Atazanavir	Everolimus	Ridaforolimus
Atorvastatin	Felodipine	Romidepsin
Avanafil	Fentanyl	Saquinavir
Bexarotene	Fluticasone	Sildenafil
BIRL 355	Gefitinib	Simeprevir
Bortezomib	Halofantrine	Simvastatin
Bosutinib	Ibrutinib	Sirolimus
Brecanavir	Ifosfamide	Tacrolimus
Brotizolam	Imatinib	Temsirolimus
Budesonide	Indinavir	Terfenadine
Bupirone	Ironotecan	Ticagrelor
Capravirine	Ivacaftor	Theophylline
Carbamazepine	Ixabepilone	Thioridazine
Casopitant	L-771,688	Thiotepa
Cisapride,	Lapatinib	Tilidine
Conivaptan	Levomethadyl (LAAM)	Tipranavir
Cyclophosphamide	Lomitapide	Tolvaptan
Cyclosporine	Lopinavir	Triazolam
Danoprevir	Lovastatin	Tretinoin
Darifenacin	Lurasidone	Ulipristal
Darunavir	Maraviroc,	Vardenafil
Dasatinib	Midazolam	Vicriviroc
Dihydroergotamine	Midostaurin	Voclosporin
Disopyramide	Mosapride	
Dronedarone	Neratinib	
Docetaxol	Nilotinib	

CYP2C19 Sensitive Substrates or Substrates with a Narrow Therapeutic Range

Diazepam
Gliclazide
Lansoprazole
(R)-Lansoprazole
(S)-Lansoprazole
(S)-Mephenytoin
(R)-Mephobarbital
Omeprazole
(R)-Omeprazole
Pantoprazole
(+)-Pantoprazole
Rabeprazole
Tilidine

CYP1A2 Sensitive Substrates or Substrates with a Narrow Therapeutic Range

Alosetron	Tacrine
Caffeine	Theophylline
Duloxetine	Tizanidine
Melatonin	
Ramelteon	

P-gp Substrates

Colchicine
Digoxin
Fexofenadine
Indinavir
Paclitaxel
Topotecan
Vincristine

If a patient requires initiation of digoxin during the study, or is already receiving treatment with digoxin, monitoring of digoxin levels is recommended according to local practice (as the levels of digoxin may increase). Monitoring of digoxin levels is also recommended when the patient has completed dosing with study treatment (as the levels of digoxin may then decrease).

P-gp Inhibitors (Strong)

Cyclosporine
Elacridar
Erythromycin
Itraconazole
Ketoconazole
LY335979Quinidine
Ritonavir
Valspodar
Verapamil

BCRP Substrates

Daunorubicin
Doxorubicin
Rosuvastatin
Sulfasalazine
Topotecan

